2.6 The Intervention

The intervention group will received 15 minute motivational interviewing in four session once a month and one session face-to-face education with booklet at the first motivational interviewing based on Watson's Theory of Human Caring before the hemodialysis session in a separate room in the hemodialysis unit.

Motivational Interviewing: The semi-structured interview based on Watson's Theory of Human Caring according to the principles of motivational interviewing such as open-ended questions, affirmation, reflection, summaries and speaking change will perform. In the motivational interviewing sessions, the agenda will set for the individuals to talk about their current concerns about fluid intake, diet and drug management, and physical, psychological and social support problems. It will aimed to reveal the individuals' personnel goals to improve their adherence to treatment and the obstacles they perceived to achieve these goals. By working with the ambivalence of the individuals, supporting their optimism and self-efficacy and positive changes, individuals will enable to determine their own solutions. In addition, individuals will support for the maintaining of behavior change.

Education: The education will apply face-to-face in one session for 30 minutes in the first motivational interviewing and an education booklet will give to the participants. The education booklet has been prepared by the researcher, according to evidence-based guidelines, literature search and result of study (<https://rb.gy/nxkgf4>, Accessed date: 24.11.2017; <https://rb.gy/totnpp>, Accessed date: 27.11.2017). The education booklet was evaluated by 10 experts in the field of nephrology and hemodialysis according to Discern guide. The educational booklet includes sections on kidneys, kidney functions, causes, symptoms, stages and treatment of chronic kidney disease (CKD), nutrition in hemodialysis, fluid intake, drugs, hemodialysis related problems, laboratory parameters.

Conceptual-theoretical-empirical (C-T-E) system-based nursing practice was used in the study. The C-T-E structure provide a purposeful and systematic process for nursing practice (Fawcett, 2005).

2.7 Control Group

The control group will receive routine hemodialysis treatment and nursing care in the hemodialysis unit. Routine nursing care consisted of dietary recommendations for high laboratory parameters and recommendations for patients' needs. The control group will receive face-to-face education for 30 minutes and education booklet at the 12th week.

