2.3. Sample Size Calculation

In this study, the sample size was calculated based on the “The Scale for Dietary Behaviors in Hemodialysis Patients” used in a similar study (Düzalan & Pakyüz, 2018). A total of 70 individuals receiving hemodialysis treatment, 35 patients in each group, were included in the study based on a common type-I error rate of 0.05, the effect size rate of 0.80 and estimated loss to follow-up of 10%.

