2.6. Outcomes

This section will present the outcomes investigated to answer the study aims and objectives. The analyses are described in section 3 Analyses.

- Adherence to fluid intake: it will be measured at baseline and 12th week using Fluid Control in Hemodialysis Patients Scale.
- Adherence to diet: it will be measured at baseline and 12th week using The Scale for Dietary Behaviors in Hemodialysis Patients.
- Adherence to drug management: it will be measured at baseline and 12th week using Modified Morisky Scale.
- Patient satisfaction: it will be measured at 12th week in the intervention group using Watson Caritas Patient Score and Motivational Interviewing Evaluation Form.
- Quality of life: it will be measured at baseline and 12th week using Kidney Disease Quality of Life-36 Scale.
- Physical parameter: it will be measured at baseline and 12th week.

Physical Parameters

- Blood Pressure
- BMI
- Glucose mg/dL
- BUN mg/dL
- Creatinine mg/dL
- Albumin g/dL
- Potassium mEq/L

- Phosphorus mEq/L
- Hematocrit %
- Hemoglobin g/dL
- Total Protein mg/dL
- Sodium mEq/L
- Calcium mEq/L

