3. ANALYSIS

The data were analysed with the IBM Statistical Package for Social Science (SPSS) for Windows version 25 (IBM, 2017). The normality test was performed with the graphical assessment, skewness and kurtosis test. Descriptive statistics for normally distributed numerical variables were presented as mean, standard deviations, n (%) or minimum-maximum. While evaluating statistical significance, it was considered according to the p value of <0.05 .

Adherence to fluid intake, diet and drug management, physical parameters and quality of life will compare intervention groups (motivational interviewing and education based Watson's Theory of Human Caring vs control treatment) on their mean change between baseline and 12 weeks using independent sample t-test. In addition, effect size will evaluated by calculator for student's t-test using G-Power programme. To identify the relationship of the change adherence to fluid intake, diet and drug management, physical parameters and quality of life with other variables such as group and demographic variables will use multivariate linear regression.

Patiens satisfaction will analyzed using descriptive analysis such as n (%) or minimum-maximum.

References

Düzalan, Ö. B., & Pakyüz, S. Ç. (2018). Educational interventions for improved diet and fluid management in haemodialysis patients: An interventional study. *Journal of Pakistan Medical Association*, 68(4), 532-537.

Fawcett, J. (2005). Watson's Theory of Human Care. In J. Fawcett (Ed.), *Contemporary Nursing Knowledge an Analysis and Evaluation of Nursing Models and Theories* (pp. 553-599). Philadelphia: F.A. Davis Company.

IBM. (2017). SPSS version 25.0. New York: IBM Corporation.

Luyckx, V. A., Tonelli, M., & Stanifer, J. W. (2018). The global burden of kidney disease and the sustainable development goals. *Bulletin of the World Health Organization*, 96(6), 414-422. doi:10.2471%2FBLT.17.206441

Naalweh, K. S., Barakat, M. A., Sweileh, M. W., Al-Jabi, S. W., Sweileh, W. M., & Sa'ed, H. Z. (2017). Treatment adherence and perception in patients on maintenance hemodialysis: A cross-sectional study from Palestine. *BMC Nephrology*, 18(1), 178-186. doi:10.1186/s12882-017-0598-2

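### Does placing the outcome, the control group's education and the fourth interview all around week 12 undermine the comparison?

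*Combined protocol and SAP*

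**What the plan says.** The document is a combined protocol and SAP, in which two sections carry the number 2.6.

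- **2.6 The Intervention:** the intervention group receives "15 minute motivational interviewing in four session once a month". The teaching component comes at the start: "The education will apply face-to-face in one session for 30 minutes in the first motivational interviewing", together with a booklet. No week is given for any session.
- **2.7 Control Group:** controls have routine hemodialysis treatment and nursing care. The section then adds: "The control group will receive face-to-face education for 30 minutes and education booklet at the 12th week".
- **2.6. Outcomes:** for diet, the scale on which the sample size rests, "it will be measured at baseline and 12th week using The Scale for Dietary Behaviors in Hemodialysis Patients". Fluid adherence, drug adherence, quality of life and the physical parameters have the same two time points. For satisfaction, "it will be measured at 12th week in the intervention group using Watson Caritas Patient Score and Motivational Interviewing Evaluation Form".
- **3. ANALYSIS:** groups are compared on "mean change between baseline and 12 weeks using independent sample t-test".

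No section gives a visit window, says whether the week-12 measurement comes before the control group's education, or places it relative to the fourth interview.

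**The concern.** Three events meet at week 12: the outcome measurement, the teaching of controls with a component of the tested intervention, and, at the earliest on the ordinary reading, the last interview.

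Two things could go wrong.

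- **Dilution in controls.** The adherence and quality-of-life outcomes are questionnaires, and the booklet covers nutrition, fluid intake and drugs. Controls who were taught before answering might shift their answers, which would narrow the difference between groups.
- **Incomplete exposure in the intervention group.** If the fourth interview falls on or after the measurement, the result would be credited to four sessions when three had had time to act. Satisfaction would also be rated before the programme was finished.

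At stake would be power on the self-reported outcomes and an accurate description of what was tested.

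**Working it through.** **1. When does the fourth interview fall?** Four monthly sessions span three intervals, so the week of session 4 = start week + 3 × (month length in days) ÷ 7. The plan gives no month length, so three are assumed. With session 1 at baseline (week 0):

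| Month taken as | Calculation | Session 4 |
|---|---|---|
| 28 days | 3 × 28 ÷ 7 | week 12.0 |
| 30 days | 3 × 30 ÷ 7 | week 12.9 |
| 365.25 ÷ 12 = 30.44 days | 3 × 30.44 ÷ 7 | week 13.0 |

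A start one week after baseline adds one week to each. In the other direction, one session in each calendar month, spaced as tightly as possible, would fit in about 8.6 weeks. The wording therefore does not force the fourth interview to fall after the measurement. If the 12th week means the whole week, the measurement can follow a week-12 interview by some days.

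**2. Can the sections be read together?** Yes. With four-week months, the interviews fall at weeks 0, 4, 8 and 12, the measurement closes the schedule, and controls are then offered the education. Three features support this order, though none proves it:

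- The control condition is defined as routine care, and the analysis contrasts the intervention with control treatment. Education placed at the final assessment time reads most naturally as education deferred until follow-up is complete.
- The week-12 satisfaction measures include a form evaluating the motivational interviewing, which points to assessment at the end of the sessions.
- The hypotheses in 2.1 promise no interval between the end of the intervention and the outcome. Measuring at the end of treatment is a legitimate choice.

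**3. How large could dilution be?** The planning inputs are "common type-I error rate of 0.05, the effect size rate of 0.80 and estimated loss to follow-up of 10" per cent, with 35 patients per group. The total of 70 cannot be reproduced uniquely, because power and sidedness are not stated. Taking 0.80 as the standardised difference d and a two-sided test (both assumptions), t-test power is 91% with 35 per group. With 10% loss, 35 × 0.9 = 31.5, taken as 31, and power is 87%.

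Let f be the share of the effect that control education would reproduce before assessment. Then the diluted difference is 0.80 × (1 − f), the noncentrality is that difference × √(n/2), and there are 2n − 2 = 60 degrees of freedom for n = 31:

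| f (assumed) | Difference | Power, 31 per group |
|---|---|---|
| 0 | 0.80 | 87% |
| 10% | 0.72 | 80% |
| 20% | 0.64 | 70% |
| 25% | 0.60 | 64% |
| 30% | 0.56 | 58% |
| 50% | 0.40 | 34% |

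Nothing in the documents supplies f, so the table shows sensitivity to an assumption and is not an estimate. The upper rows of f would need one 30-minute session in the assessment week to match a large part of an effect planned for four interviews plus education over about 12 weeks.

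**4. Are the two worries consistent?** Not at full strength. If contact in the assessment week has no time to act, teaching controls that week dilutes nothing. If it acts at once, a fourth interview that week is not wasted. They can be partly reconciled by outcome type, since questionnaires can respond quickly while laboratory values and BMI cannot. That leaves only the questionnaires exposed to dilution.

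**The case for a change.** The strongest reply is that a plan should not depend on a reader guessing the order. Section 2.7 and the outcomes section name the same week, and the taught material matches the subjects of the adherence scales. Section 2.5 describes no blinded outcome assessor, so nothing else in the document protects the order. One sentence would settle it at no cost. On a calendar-month reading, some patients could have had three interviews at the endpoint and others four.

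Much of this stands as description. The order is unstated, the coincidence is in the text, and the questionnaires would be exposed if controls were taught first. The calendar-month reading is also possible.

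It does not show that the sections contradict each other or that the planned comparison is unsound. Silence on sequence within a week is not an instruction to teach first, and teaching controls before their final assessment would run against the routine-care condition the plan defines. Dilution, if it occurred, would shrink the contrast and could not manufacture a benefit. An interview falling after the measurement would change how many sessions the result describes, while both groups would still be compared at the same nominal time as randomised.

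**Conclusion.** The concern does not call for a change. The remaining gap is the unwritten order, within week 12, of measurement, control education and, at four-week spacing, the fourth interview. Investigators would very likely fill it sensibly by completing the assessment before controls receive the deferred education. The result is a sound end-of-treatment randomised comparison.

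The size of any harm cannot be derived from the documents. For self-report it depends on an assumed share f and on an order the plan does not prescribe. For laboratory values and BMI it should be small. The timing discrepancy is zero with four-week months and about one week (13.0 − 12.0) with calendar months, taking the first interview at baseline.

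The conclusion rests on two assumptions: that the control education is deferred education, and that week 12 is meant as the end of the intervention schedule. Both fit the text, and neither is stated outright. A trial report that gives the actual order of events and the number of interviews delivered before assessment would let readers confirm them.

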2.6. Outcomes

This section will present the outcomes investigated to answer the study aims and objectives. The analyses are described in section 3 Analyses.

- Adherence to fluid intake: it will be measured at baseline and 12th week using Fluid Control in Hemodialysis Patients Scale.
- Adherence to diet: it will be measured at baseline and 12th week using The Scale for Dietary Behaviors in Hemodialysis Patients.
- Adherence to drug management: it will be measured at baseline and 12th week using Modified Morisky Scale.
- Patient satisfaction: it will be measured at 12th week in the intervention group using Watson Caritas Patient Score and Motivational Interviewing Evaluation Form.
- Quality of life: it will be measured at baseline and 12th week using Kidney Disease Quality of Life-36 Scale.
- Physical parameter: it will be measured at baseline and 12th week.

Physical Parameters

- Blood Pressure
- BMI
- Glucose mg/dL
- BUN mg/dL
- Creatinine mg/dL
- Albumin g/dL
- Potassium mEq/L

- Phosphorus mEq/L
- Hematocrit %
- Hemoglobin g/dL
- Total Protein mg/dL
- Sodium mEq/L
- Calcium mEq/L

3. ANALYSIS

The data were analysed with the IBM Statistical Package for Social Science (SPSS) for Windows version 25 (IBM, 2017). The normality test was performed with the graphical assessment, skewness and kurtosis test. Descriptive statistics for normally distributed numerical variables were presented as mean, standard deviations, n (%) or minimum-maximum. While evaluating statistical significance, it was considered according to the p value of <0.05 .

Adherence to fluid intake, diet and drug management, physical parameters and quality of life will compare intervention groups (motivational interviewing and education based Watson's Theory of Human Caring vs control treatment) on their mean change between baseline and 12 weeks using independent sample t-test. In addition, effect size will evaluated by calculator for student's t-test using G-Power programme. To identify the relationship of the change adherence to fluid intake, diet and drug management, physical parameters and quality of life with other variables such as group and demographic variables will use multivariate linear regression.

Patiens satisfaction will analyzed using descriptive analysis such as n (%) or minimum-maximum.

References

Düzalan, Ö. B., & Pakyüz, S. Ç. (2018). Educational interventions for improved diet and fluid management in haemodialysis patients: An interventional study. *Journal of Pakistan Medical Association*, 68(4), 532-537.

Fawcett, J. (2005). Watson's Theory of Human Care. In J. Fawcett (Ed.), *Contemporary Nursing Knowledge an Analysis and Evaluation of Nursing Models and Theories* (pp. 553-599). Philadelphia: F.A. Davis Company.

IBM. (2017). SPSS version 25.0. New York: IBM Corporation.

Luyckx, V. A., Tonelli, M., & Stanifer, J. W. (2018). The global burden of kidney disease and the sustainable development goals. *Bulletin of the World Health Organization*, 96(6), 414-422. doi:10.2471%2FBLT.17.206441

Naalweh, K. S., Barakat, M. A., Sweileh, M. W., Al-Jabi, S. W., Sweileh, W. M., & Sa'ed, H. Z. (2017). Treatment adherence and perception in patients on maintenance hemodialysis: A cross-sectional study from Palestine. *BMC Nephrology*, 18(1), 178-186. doi:10.1186/s12882-017-0598-2

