2. STUDY DESIGN

2.1 Objective and Hypothesis

The aims of the study were to evaluate the effectiveness of Motivational interviewing and education based on Watson's Theory Of Human Caring on adherence to treatment, satisfaction and QOL in individuals receiving hemodialysis treatment. We hypothesized that intervention group who received Motivational interviewing and education based on Watson's Theory of Human Caring would increase (a) adherence to fluid intake, (b) adherence to diet, (c) adherence to drug management, (d) QOL compared to the control group and (e)

intervention group who receiving motivational interviewing and education based on Watson's Theory of Human Caring would satisfied with introduced intervention.

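### Thirteen physical parameters with no hypothesis, direction or exploratory label are tested between arms at 0.05 as outcomes that answer the study aims

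*Combined protocol and SAP*

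**What the plan says.** Section 2.1 hypothesises that the intervention "would increase (a) adherence to fluid intake, (b) adherence to diet, (c) adherence to drug management, (d) QOL compared to the control group", and adds hypothesis (e), that the intervention group "would satisfied with introduced intervention". No physical or laboratory parameter appears in the aim or in any of the five hypotheses.

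Section 2.6 (Outcomes) opens with "This section will present the outcomes investigated to answer the study aims and objectives". Its list includes "Physical parameter: it will be measured at baseline and 12th week", followed by 13 items: blood pressure, BMI, glucose, BUN, creatinine, albumin, potassium, phosphorus, hematocrit, hemoglobin, total protein, sodium and calcium. Neither these nor any other outcome is called primary, secondary or exploratory.

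Section 3 names the physical parameters together with the adherence and quality-of-life outcomes ("Adherence to fluid intake, diet and drug management, physical parameters and quality of life will compare intervention groups"), compares the arms "on their mean change between baseline and 12 weeks using independent sample t-test", and sets one criterion: "While evaluating statistical significance, it was considered according to the p value of <0.05". It gives no multiplicity rule. It then relates the change in the same outcomes, physical parameters included, to other factors: "with other variables such as group and demographic variables will use multivariate linear regression".

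**The concern.** The hypothesised outcomes have a direction: adherence and quality of life are expected to rise. The physical parameters have none, and no parameter is tied to a particular hypothesis. Yet they have the same standing as the hypothesised outcomes, the same test and the same threshold. Under these rules one significant parameter out of 13, moving either way, counts as a result on the study aims, and its interpretation can be chosen once the result is known. Ranking or adjusting only hypotheses (a) to (d) would leave these 13 tests as they are.

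What is at stake is interpretation. The adherence and quality-of-life outcomes are scale scores, and Section 2.5 says the researcher delivers the intervention. An isolated laboratory difference could be read as independent support for an effect when it is only chance.

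**Working it through.** **Inputs from the documents**
- Threshold per test: 0.05 (Section 3).
- Test: independent-samples t-test on change from baseline to week 12 (Section 3).
- Parameters: 13, of which 11 are laboratory values (Section 2.6, Outcomes).

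**Assumptions**
- Tests are two-sided. Section 3 gives only the p-value threshold.
- Correlations between the test statistics are 0, 0.2, 0.5 or 0.8, common to all pairs. The documents give none.
- Blood pressure counts as one test. Separate systolic and diastolic tests would make 14.

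The plan states no error rate for the set of parameters, so it has no figure of its own to reproduce. The only reference is 0.05 for a single test.

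**Independent tests, no true effect.** The chance of at least one p<0.05 among k tests is 1 − 0.95^k.
- 13 parameters: 1 − 0.95^13 = 0.487.
- 11 laboratory values alone: 1 − 0.95^11 = 0.431.
- 14 tests: 1 − 0.95^14 = 0.512.

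**Correlated tests.** For equicorrelated normal test statistics with correlation r and threshold |z| > 1.96:

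| Set | r = 0 | r = 0.2 | r = 0.5 | r = 0.8 |
|---|---|---|---|---|
| 13 parameters | 49% | 45% | 33% | 19% |
| 14 tests | 51% | 47% | 35% | 20% |
| 11 laboratory values | 43% | 40% | 30% | 18% |

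A simulation of actual t-tests with 35 patients per arm agrees for 13 parameters: 49% at r = 0, 46% at 0.2 and 34% at 0.5. If only natural pairs are correlated (hemoglobin with hematocrit 0.95, BUN with creatinine 0.6, albumin with total protein 0.6, potassium with phosphorus 0.3, all assumed), it gives 47%.

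**One favourable direction only.** If a single direction per parameter would count as benefit, each test has a 0.025 chance of a false favourable result: 1 − 0.975^13 = 0.280. At r = 0.2 this is 24%, and at r = 0.5 it is 17%.

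**Expected false positives.** 13 × 0.05 = 0.65 (14 × 0.05 = 0.70), whatever the correlation.

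None of these figures counts the regression, which gives a further group coefficient for each parameter.

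**The case against.** The strongest reply is that this is one instance of a general gap. No outcome is named primary and nothing in Section 3 is adjusted, so a full hierarchy that placed every outcome would cover these parameters too. That is right, and if such a hierarchy is written the two changes should be made together. The point still has to be made for these parameters, because they alone among the tested outcomes lack a hypothesis and a direction. A hierarchy confined to (a) to (d) would miss them.

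Second, the harm can be overstated. A reader might infer that a false laboratory finding is likely. For 13 tests the range is 19% to 49%. It passes one half only with 14 independent tests, and it is lower for laboratory values alone or for favourable results alone. A reader might also infer that this is the most probable false claim in the trial. The documents do not show that: the regressions on group and demographic variables may involve more tests, and no comparison is possible with the risk of bias in the scale scores.

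Third, nothing in the documents says that a laboratory result will be presented as objective confirmation. That it could be is as far as the text goes. Section 3 also plans effect sizes, so reporting need not rest on p-values alone. An effect size does not change a parameter's standing as an outcome that answers the aims.

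Finally, one may assume that these are evident markers of adherence, potassium and phosphorus for diet in particular. The documents make no such link. Section 2.7 mentions dietary advice for high laboratory values only in general, and as part of routine care in the control group.

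**Conclusion.** The concern holds as a matter of status and interpretation. The plan tests 13 parameters that have no hypothesis, direction or exploratory label, and treats each as evidence on the aims at 0.05. With no true effect and two-sided tests, the chance of at least one significant t-test is about 49% under independence and about 19% at a correlation of 0.8, roughly 4 to 10 times the nominal 0.05. Counting only one favourable direction per parameter, it is 28% under independence. The count of 13 and the threshold come from the documents. Sidedness, the correlations and any split of blood pressure are assumptions. The change should be made, because it alters what the trial may conclude from an isolated result. It does not call the tests of the hypothesised outcomes into question.

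**What to change.** 1. In Section 2.6 (Outcomes), list the physical parameters separately and label them exploratory.
2. In Section 3, report each as the between-arm difference in change with its 95% confidence interval, and state that no effectiveness claim rests on them.
3. In Section 3, give the same exploratory status to the group coefficients from the regressions on the physical parameters. Otherwise the regression would bring back a p-value for each one.
4. If the sponsor wants objective support for a hypothesis, it should name in advance one or two parameters already collected, of its own choice, with the hypothesis each supports and the expected direction. Only those would be tested, Holm-adjusted at 0.05, as supportive evidence.

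The cost is a few sentences, with no new data or patients. The one loss is that an isolated significant physical or laboratory value can no longer be claimed as an effect.

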2.4. Inclusion and Exclusion Criteria

Inclusion criteria of the study were as follows:

- participants were individuals aged ≥ 18 years,
- received hemodialysis for at least 3 months,
- had 1 and over from Diet and Fluid Non-Adherence Questionnaire (DDFQ) total score,
- had 0 or 1 score from 1., 2. and 6. questions or 3., 4. and 5. questions in the Modified Morisky Scale (MMS),
- willing to participate,
- participants without language or communication barriers.

The exclusion criteria of the study were as follows:

- The participants diagnosed with psychiatric illness or malignancy were excluded from the study.

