2.5. Randomization and blinding

The simple randomizaton method will used. Individuals receiving hemodialysis who met the inclusion criteria, agreed to participate in the study and signed the informed consent form were divided into either a intervention group or control group by coded randomization by researcher. An independent, blind statistician who will not involved in the research process

prepared the random number table with SAS package 9.4. It will not possible allocation concealment as the intervention was performed by the researcher who received motivational interviewing and education. The researcher will not participate in the data analysis, the analyzes will made by an expert statistician.

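### The between-group test on change from baseline is valid but leaves out the baseline already collected; adjusting for it (ANCOVA) would usually tighten the estimates, by an amount the documents do not allow us to fix

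*Combined protocol and SAP*

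**What the plan says.** Section 3 compares the two groups on fluid, diet and drug adherence, physical parameters and quality of life "on their mean change between baseline and 12 weeks using independent sample t-test". No covariate enters this test. The standardised effect follows the same route: "effect size will evaluated by calculator for student's t-test using G-Power programme".

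Section 3 also plans a second model, which relates the change in these outcomes "with other variables such as group and demographic variables will use multivariate linear regression". That covariate list is open-ended. It does not name the outcome's own baseline value, and this model is not the stated between-group comparison.

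Section 2.6 (Outcomes) shows that the baselines exist. For diet, "it will be measured at baseline and 12th week using The Scale for Dietary Behaviors in Hemodialysis Patients"; for drugs, "Adherence to drug management: it will be measured at baseline and 12th week using Modified Morisky Scale". Fluid adherence, quality of life and the physical parameters follow the same two-visit schedule. Patient satisfaction is measured in the intervention group only and is not part of this point.

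Three other places bear on the size of the effect:
- Section 2.3 plans 35 patients per group, with "the effect size rate of 0.80 and estimated loss to follow-up of 10" per cent.
- Section 2.5 says "The simple randomizaton method will used" and describes no stratification.
- Section 2.4 selects patients on their adherence scores, for example those who "had 1 and over from Diet and Fluid Non-Adherence Questionnaire (DDFQ) total score".

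**The concern.** Subtracting the baseline assumes that each unit of baseline difference carries over in full to week 12. The true slope of the 12-week value on baseline is rho × k. If it is below 1, the change score over-corrects for a chance baseline difference; if above 1, it under-corrects. In both cases it carries variance that ANCOVA would remove. With few patients per arm, that means wider confidence intervals and lower power than the same data allow. Simple randomisation also leaves room for the arms to start apart on one or more of the many outcomes.

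**Working it through.** **Inputs from the documents.** 35 per arm and 10% loss (section 2.3): 35 × 0.90 = 31.5, taken as 31. Alpha is 0.05; two-sided is assumed, because sidedness is not stated.

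**Inputs assumed.** rho from 0.3 to 0.9, and k = 0.8, 1 and 1.3. Neither quantity is in the documents.

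**The plan's own figure.** The total of 70 cannot be rebuilt from what is stated, because no power is given. Reading 0.80 as a standardised effect, the t-test calculation with 10% loss gives 58 at 80% power, 68 at 85% and 76 at 90%. The 0.80 could also be a mislabelled power. The variance ratios and interval widths below do not depend on this; the power figures do.

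**Variances.** With baseline SD 1 and 12-week SD k:
- Change score: 1 + k² − 2·rho·k
- ANCOVA: k²(1 − rho²)
- Difference: (1 − rho·k)², which is never negative and is zero only when rho × k = 1

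Example, k = 1 and rho = 0.5: 0.75 / 1.00 = 0.75.

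**Cost of estimating the slope.** The variance is multiplied on average by 1 + 1/(62 − 4) = 1.017, and the t quantile uses 59 instead of 60 degrees of freedom (factor 1.0003). The CI width ratio is √(variance ratio × 1.017) × 1.0003.

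The power column takes a true effect of 0.80 change-score SD, for which the planned t-test has 87.3% power.

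| k | rho | variance ratio | CI width ratio | ANCOVA power |
|---|---|---|---|---|
| 0.8 | 0.3 | 0.50 | 0.71 | 99% |
| 0.8 | 0.5 | 0.57 | 0.76 | 98% |
| 0.8 | 0.7 | 0.63 | 0.80 | 97% |
| 0.8 | 0.9 | 0.61 | 0.79 | 98% |
| 1 | 0.3 | 0.65 | 0.81 | 97% |
| 1 | 0.5 | 0.75 | 0.87 | 94% |
| 1 | 0.7 | 0.85 | 0.93 | 92% |
| 1 | 0.9 | 0.95 | 0.98 | 88% |
| 1.3 | 0.3 | 0.81 | 0.905 | 93% |
| 1.3 | 0.5 | 0.91 | 0.96 | 90% |
| 1.3 | 0.7 | 0.99 | 1.004 | 87% |
| 1.3 | 0.9 | 0.92 | 0.97 | 89% |

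**Where ANCOVA gains nothing.** If rho × k = 1, the width ratio averages √1.017 × 1.0003 = 1.009, and power is 86.7% against 87.3%. Single trials vary around that average: in simulation at slope 1, about 5% had intervals at least 3.6% wider.

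**Chance imbalance.** The baseline difference between arms has SD √(2/35) = 0.239 baseline SD. A gap of at least 0.25 SD is then 1.05 standard errors, a probability of about 30% per outcome (32% at 31 per arm). A gap of exactly 0.25 moves the change-score estimate by (rho·k − 1) × 0.25 baseline SD. For rho 0.3, 0.5, 0.7 and 0.9 this is −0.175, −0.125, −0.075 and −0.025 at k = 1, and −0.15, −0.09, −0.02 and +0.04 at k = 1.3.

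**Validity.** In 20,000 simulated null trials per setting (63 completers, simple randomisation), type I error was 4.8 to 5.3% for the t-test and 5.0 to 5.2% for ANCOVA.

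**The case against.** The strongest reply is that the plan contains no error. A t-test on change is an accepted analysis, it is unbiased over randomisation, and it suits hypotheses worded as increases. All of that stands. A reader might infer from this point that the planned test is biased or gives false positives; neither the algebra nor the simulation supports that. Section 2.5 says allocation concealment will not be possible, but that is a separate matter which neither analysis cures.

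The second reply is that the size rests wholly on assumed rho and k. This also stands, and the entry rules push towards the less favourable part of the range. Selecting non-adherent patients restricts the baseline spread, so k above 1 is plausible for the adherence scales, where the gain is smaller. Nothing in the documents argues for k = 0.8, so its large gains should not be taken as the expectation. A low rho does not guarantee a large gain either: at k = 1.5 and rho = 0.3 the variance ratio is 0.87. Nor does a high rho guarantee a small one: at k = 1.5 and rho = 0.9 it is 0.78. What governs the gain is how far rho × k lies from 1, relative to the variance of the change.

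The third reply is that the planned regression could already include the baseline, since its list is open. It could, and a reader should not infer that baseline adjustment is ruled out. But the plan does not commit to it, and that regression is not the stated between-group test.

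Lastly, the Modified Morisky Scale has few levels. That makes the t-test and linear ANCOVA alike approximations, so it does not favour either.

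**Conclusion.** The point holds as one of efficiency, not validity. No planned model commits to using the baselines the trial collects, and the stated between-group test fixes their slope at 1.

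At 31 per arm and rho 0.3 to 0.9, adjustment would narrow confidence intervals by about 19% down to 2% if k = 1. If k = 1.3, the result runs from 9.5% narrower to 0.4% wider. These are assumption ranges, not forecasts for this trial.

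It would be too strong to say that ANCOVA always gives a narrower interval or that its cost never exceeds 1%. The 0.9% figure is an average at rho × k = 1, and a single trial can lose more. Nor do the documents show that the trial is underpowered: if 0.80 is an effect in change-score SDs, the planned test has 87% power. The case for adjusting is that the average loss is small and bounded, the possible gain is considerable, and rho and k are unknown.

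**What to change.** Replace the t-test sentence in section 3 with wording such as:

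> *Fluid, diet and drug adherence, each physical parameter and quality of life will each be compared between groups by linear regression of the 12-week value on randomised group and that outcome's baseline value (ANCOVA). The adjusted mean difference will be reported with its 95% confidence interval.*

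If change is preferred as the dependent variable, regress change on group and baseline; the group effect and its standard error are identical. In the regression with demographic variables, name the outcome's baseline value as a covariate. Whatever standardised effect size is reported, state which SD it uses.

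The cost is SAP wording, one degree of freedom and on average about 1.7% of variance. No new data are needed, and SPSS fits the model.

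The timing needs checking. Sections 2.3 and 3 are partly in the past tense, and the mixed tenses do not settle whether outcome data have been seen. If they have, keep the t-test as the main result and report ANCOVA beside it, labelled post hoc.
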